4.1.2 Exclusion criteria

- Previous assignment to treatment during this study. Subjects permanently withdrawn from study participation will not be allowed to re-enter study.
- Other investigational treatment during or within 21 days before starting study treatment
- Child Pugh B or C
- Uncontrolled hypertension (systolic pressure >140 mm Hg or diastolic pressure > 90 mm Hg [NCI-CTCAE v4.0] on repeated measurement) despite optimal medical management.
- Active or clinically significant cardiac disease including:
 - Congestive heart failure – New York Heart Association (NYHA) $>$ Class II.
 - Active coronary artery disease.
 - Cardiac arrhythmias requiring anti-arrhythmic therapy other than beta blockers or digoxin.
 - Unstable angina (anginal symptoms at rest), new-onset angina within 3 months, or myocardial infarction within 6 months.
- Evidence or history of bleeding diathesis or coagulopathy.

- Any hemorrhage or bleeding event \geq NCI CTCAE Grade 3 within 4 weeks prior to start of study medication.
- Subjects with thrombotic, embolic, venous, or arterial events, such as cerebrovascular accident (including transient ischemic attacks) deep vein thrombosis or pulmonary embolism within 6 months of informed consent.
- No active malignancy except for nonmelanoma skin cancer or *in situ* cervical cancer. Subjects surviving a cancer that was curatively treated and without evidence of disease for more than 3 years before the trial are allowed. All cancer treatments must be completed at least 3 years prior to study entry (i.e., signature date of the informed consent form).
- Patients with pheochromocytoma.
- Known history of human immunodeficiency virus (HIV) infection or current chronic or active hepatitis B or C infection requiring treatment with antiviral therapy.
- Ongoing infection $>$ Grade 2 NCI-CTCAE v4.0.
- Symptomatic metastatic brain or meningeal tumors.
- Presence of a non-healing wound, non-healing ulcer, or bone fracture.
- Renal failure requiring hemo-or peritoneal dialysis.
- Patients with seizure disorder requiring medication.
- Persistent proteinuria \geq Grade 3 NCI-CTCAE v4.0 ($>$ 3.5 g/24 hrs, measured by urine protein:creatinine ratio on a random urine sample).
- Interstitial lung disease with ongoing signs and symptoms at the time of informed consent.
- Pleural effusion or ascites that causes respiratory compromise (\geq NCI-CTCAE version 4.0 Grade 2 dyspnea).
- History of organ allograft (including corneal transplant).
- Known or suspected allergy or hypersensitivity to any of the study drugs, study drug classes, or excipients of the formulations given during the course of this trial.
- Any malabsorption condition.
- Women who are pregnant or breast-feeding.
- Any condition which, in the investigator's opinion, makes the subject unsuitable for trial participation.
- Substance abuse, medical, psychological or social conditions that may interfere with the subject's participation in the study or evaluation of the study results.

4.1.3 Excluded therapies and medications, previous and concomitant

- Concurrent anti-cancer therapy (chemotherapy, radiation therapy, surgery, immunotherapy, biologic therapy, or tumor embolization) other than study treatment
- Prior use of regorafenib or other anti VEGF drugs.
- Concurrent use of another investigational drug or device therapy (i.e., outside of study treatment) during, or within 21 days of trial entry (signing of the informed consent form).
- Major surgical procedure, open biopsy, or significant traumatic injury within 28 days before start of study medication.
- Use of any herbal remedy (e.g. St. John's wort [*Hypericum perforatum*])

4.2 Withdrawal of subjects from study

4.2.1 Withdrawal

Subjects **must be withdrawn from the trial** (treatment and procedures) for the following reasons:

- Subject withdraws consent from study treatment and study procedures. A subject must be removed from the trial at his/her own request or at the request of his/her legally acceptable representative. At any time during the trial and without giving reasons, a subject may decline to participate further. The subject will not suffer any disadvantage as a result.
- Pregnancy. Pregnancy will be reported as an SAE. (Note: subjects who have been withdrawn from treatment with study drug because of pregnancy should not undergo CT scans [with contrast]/MRI or bone scans while pregnant.)
- If, in the investigator's opinion, continuation of the trial would be harmful to the subject's well-being.
- Subject is lost to follow-up.
- Progression of disease
- Death.

Subjects **may be** withdrawn from the study for the following reasons:

- The subject is non-compliant with study drug, trial procedures, or both; including the use of anti-cancer therapy not prescribed by the study protocol.

- Severe allergic reaction to regorafenib (such as exfoliative erythroderma or Grade 3 or 4 hypersensitivity reaction).
- The development of a second cancer.
- Development of an intercurrent illness or situation which would, in the judgment of the investigator, significantly affect assessments of clinical status and trial endpoints.
- Deterioration of ECOG performance status to 3 or 4.
- Use of illicit drugs or other substances that may, in the opinion of the investigator, have a reasonable chance of contributing to toxicity or otherwise skewing trial result.

Any subject removed from the trial will remain under medical supervision until discharge or transfer is medically acceptable.

In all cases, the reason for withdrawal must be recorded in the CRF and in the subject's medical records.

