5.1.4 Dose Modification for management of adverse events

5.1.4.1 Dose Reduction Levels

The starting dose of regorafenib is 160 mg once daily. Study medication will be administered on a 3 weeks on/1week off schedule [3 weeks out of every 4].

Doses will be delayed or reduced for clinically significant hematologic and non-hematologic toxicities that are related to protocol therapy according to the guidelines shown in the Dose Delays/Dose Modifications table that follows. Dose modifications will

follow predefined dose levels. Dose adjustments for hematologic toxicity are based on the blood counts obtained in preparation for the day of treatment.

The modifications of regorafenib will follow the following predefined dose levels:		
Dose level 0 (standard starting dose)	160 mg po qd	Four 40-mg tablets of regorafenib
Dose level - 1	120 mg po qd	Three 40-mg tablets of regorafenib
Dose level - 2	80 mg po qd	Two 40-mg tablets of regorafenib

If a subject experiences more than one toxicity, dose reduction should be according to the toxicity with the highest grade

In the case of two or more toxicities of the same grade, the investigator may dose reduce according to that deemed most causally related to study treatment

If more than 2 dose reductions are required, regorafenib will be discontinued and patient will need to come off of the trial. If a dose reduction has been performed, intra-subject dose re-escalation can be considered (up to the maximal 160 mg daily dose) at the discretion of the treating physician provided that the toxicity(ies) has resolved to baseline.

The following tables outline dose adjustments for toxicities related to study drug except hand-foot skin reaction, hypertension and liver function test abnormalities.

Table 6-1: Recommended dose modification for toxicities except hand-foot-skin reaction, hypertension and ALT/ST/bilirubin			
NCI-CTCAE v4.0^a	Dose Interruption	Dose Modification^b	Dose for Subsequent Cycles
Grade 0-2	Treat on time	No change	No change
Grade 3	Delay until \leq Grade 2 ^c	Reduce by 1 dose level	If toxicity remains < Grade 2, dose re-escalation can be considered at the discretion of the treating investigator. If dose is re-escalated and toxicity (\geq Grade 3) recurs, institute permanent dose reduction.
Grade 4	Delay until \leq Grade 2 ^c	Reduce by 1 dose level. Permanent discontinuation can be considered at	

		treating investigator's discretion.	

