Grade 2	1 st occurrence	Consider decreasing dose by one dose level and immediately institute supportive measures. If no improvement, interrupt therapy for a minimum of 7 days, until toxicity resolves to Grade 0-1 ^{b, c}
	No improvement within 7 days or 2 nd occurrence	Interrupt therapy until toxicity resolves to Grade 0-1. ^c When resuming treatment, treat at reduced dose level ^b
	3 rd occurrence	Interrupt therapy until toxicity resolves to Grade 0-1. ^c When resuming treatment, decrease dose by one dose level. ^{b, d}
	4 th occurrence	Discontinue therapy
Grade 3	1 st occurrence	Institute supportive measures immediately. Interrupt therapy for a minimum of 7 days until toxicity resolves to Grade 0-1. ^c When resuming treatment, decrease dose by one dose level. ^{b, d}
	2 nd occurrence	Institute supportive measures immediately. Interrupt therapy for a minimum of 7 days until toxicity resolves to Grade 0-1. ^c When resuming treatment, decrease dose by one additional dose level ^{b, d}
	3 rd occurrence	Discontinue treatment permanently.

a. More conservative management is allowed if judged medically appropriate by the investigator.
 
b. If toxicity returns to Grade 0-1 after dose reduction, dose re-escalation is permitted at the discretion of the investigator if subject has completed one cycle at reduced dose without recurrence of event.
 
c. If there is no recovery after a 4-week delay, treatment with regorafenib will be discontinued permanently.
 
d. Subjects requiring > 2 dose reductions should go off protocol therapy.
 
e. The maximum daily dose is 160 mg.
		

At first occurrence of HFSR, independent of grade, prompt institution of supportive measures such as topical emollients, low potency steroids, or urea-containing creams should be administered.

Recommended prevention/management strategies for skin toxicities consistent with HFSR are summarized below:

Control of calluses

Before initiating treatment with regorafenib:

- Check condition of hands and feet.
- Suggest a manicure/pedicure, when indicated.
- Recommend pumice stone use for callus or 'rough spot' removal.

During regorafenib treatment:

- Avoid pressure points.
- Avoid items that rub, pinch or create friction.

Use of creams

- Non-urea based creams may be applied liberally.
- Keratolytic creams (e.g. urea-based creams, salicylic acid 6%) may be used sparingly and only to affected (hyperkeratotic) areas.

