6.1 Calendar

Required studies must be done within 28 days prior to starting on the treatment.

REQUIRED STUDIES	Pre-Study	Cycle 1 +/- 2 Days				Cycle 2 +/- 2 Days				Cycle 3 ¹ +/- 2 Days				Pre-Progression Follow-Up ¹	Post-Progression Follow-Up ²
		Wk 1	Wk 2	Wk 3	Wk 4	Wk 5	Wk 6	Wk 7	Wk 8	Wk 9	Wk 10	Wk 11	Wk 12		
PHYSICAL ¹															
History and Physical Exam (informed consent)	X	X	X	X	X	X	X			X				X	X
Weight and Performance Status	X	X	X	X	X	X	X			X				X	
Toxicity Notation	X	X	X	X	X	X	X			X				X #	X #
Blood Pressure		X	X	X	X	X	X								
LABORATORY ¹															
CBC, Differential, Platelets	X	X		X		X		X		X					
CA-19-9	X									X					
Serum Chemistry ³	X	X		X		X		X		X					
U/A ⁷	X														
PT/INR	X														
X-RAYS AND SCANS ^{1, 4}															
CT/MRI for Disease Assessment ⁵	X									X				X	
EKG	X														
SPECIMEN SUBMISSION															
Blood sample (for correlatives) ⁶	X									X					
TREATMENT															
Regorafenib		X	X	X		X	X	X		X	X	X			

- 1 Protocol treatment and parameters will continue at these intervals until progression of disease or until patient has met any of the guidelines in Section 4.2.1
- 2 After off treatment following disease progression, physical assessments (with lab tests performed at the discretion of the treating investigator) should take place every 3 months for up to two years or death.
- 3 Sodium, potassium, chloride, CO₂, calcium, magnesium, phosphorus, blood urea nitrogen [BUN], creatinine, glucose, albumin, total protein, alkaline phosphatase, bilirubin [total and direct], AST, ALT

- 4 To be performed every 8 weeks until progression. Must be performed using same method as prestudy.
- 5 Scan must be performed +/- 1 week of each assessment.
- 6 Draw 1 x10mls EDTA tubes at baseline, Cycle 3 Day 1 (+/- 2 days), and at the treatment discontinuation visit if patient continues on after cycle 3 day1. (see section 13.)
7. Spot urine must not show 2+ or more protein in urine or the patient will require a repeat urine analysis. If repeat urinalysis shows 2+ protein or more, a 24- hour urine collection will be required and must show total protein excretion <3500 mg/24 hours

Toxicity should be evaluated until resolution of any adverse events.

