8.1 Sample Size Determination

Overall Survival (OS) at 6 month is the primary endpoint on this study. OS is defined in section 8.2. Dropouts/screen failures defined in section 4.2.2 and those who are lost

follow-up prior to 6 months from starting on trial except death are not evaluable for the primary endpoint, and they will be replaced by new patients. The study will test the null hypothesis of $\leq 30\%$ of OS at 6 month against the alternative of $\geq 50\%$ of OS at 6 month (HR = 0.578 under exponential model). The sample size was determined, based on the Simon's two-stage minimax design. With one-sided 10% of type I error rate and 90% statistical power, a sample of evaluable 39 will be evaluated: 28 in first stage and additional 11 in second stage. If 8 or more out of 28 survive 6 months or more, the study goes on the second stage.. REGORAFENIB will be deemed to have good activity if ≥ 16 out of 39 patients survive 6 months or more from starting on trial. The continuation of accrual may be allowed while the analysis for early stopping being conducted. We expect to accrue 2 or more patients per month among 6-7 participating institutions and will follow up patients 6 months or more.

Dropouts/screen failures defined in section 4.2.2 and those who are lost follow-up prior to 6 months from starting on trial except death, disease and severe toxicity are not evaluable for the primary endpoint, and they will be replaced by new patients

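### Section 4.2.1 withdraws patients from all trial procedures at progression, with no exception for survival follow-up, while the calendar and section 8.1 need the same patients followed for the 6-month endpoint

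*Combined protocol and SAP*

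**What the plan says.** Section 4.2.1 opens its mandatory list with "Subjects must be withdrawn from the trial (treatment and procedures) for the following reasons". One entry is "Progression of disease". The only provision there for what happens afterwards is "Any subject removed from the trial will remain under medical supervision until discharge or transfer is medically acceptable"; survival follow-up is not mentioned.

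The section 6.1 calendar has a post-progression follow-up column. Its footnote 2 says "After off treatment following disease progression, physical assessments (with lab tests performed at the discretion of the treating investigator) should take place every 3 months". These assessments stop after two years at most, or at death. Footnote 1 continues protocol treatment and parameters "until progression of disease or until patient has met any of the guidelines in Section 4.2.1".

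Section 8.1 bases the decision on 6-month survivors (continue if at least 8 of 28, active if at least 16 of 39) and plans at least 6 months of follow-up. Section 8.2 defines overall survival (OS) to death from any cause. Section 4.2.2 excludes those who leave through death, progression or severe toxicity from the dropout category.

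Section 8.1 has two sentences on patients without 6-month status. The first makes an exception only for death. The second covers those "lost follow-up prior to 6 months from starting on trial except death, disease and severe toxicity are not evaluable for the primary endpoint", so its exception is wider.

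For a patient needing more than two dose reductions, the text of 5.1.4.1 says "regorafenib will be discontinued and patient will need to come off of the trial". Footnote d of Table 6.3 says "Subjects requiring > 2 dose reductions should go off protocol therapy", and footnote c of Table 6-4 says the same in substance.

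**The concern.** One event, progression, triggers both the end of all trial procedures (4.2.1) and up to two years of scheduled assessments (calendar footnote 2). Sections 11.5 and 12.1 demand strict adherence, and a site cannot comply with both instructions.

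The conflict falls on the primary endpoint. Progressing patients who completed the first cycle stay in the evaluable 28 and 39, so whether each was alive at 6 months has to be known. A site that closes the record at progression cannot supply that. Section 9.6 does not fill the gap, because it asks for death reports only during the trial or within 30 days of the end-of-treatment visit. The dose-reduction wording raises the same question for patients who leave treatment through toxicity: off the trial could be read as ending follow-up, while off protocol therapy could not.

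**Working it through.** **1. The plan's own design.** Inputs from 8.1: null 30%, alternative 50%, one-sided 10% type I error, 90% power, 28 + 11 = 39 patients, cut-offs 8 and 16. The probability of declaring activity at true rate p is the sum over x = 8 to 28 of Bin(x; 28, p) × P(Bin(11, p) ≥ 16 − x). At p = 0.30 this gives 0.0943, and at p = 0.50 it gives 0.9001. An exhaustive minimax search returns the stated design. The design is sound if every status is known.

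**2. Unknown status, patient kept in the 39 and not counted as a survivor.** This is one possible result of the second 8.1 sentence; the documents do not say how such a patient is counted. If a share m of true 6-month survivors has unknown status, the counted rate is p(1 − m). The values of m are assumptions.

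| m | Counted rate at p = 0.50 | Power | Type I error (p = 0.30) |
|---|---|---|---|
| 0 | 0.500 | 0.900 | 0.094 |
| 5% | 0.475 | 0.834 | 0.063 |
| 10% | 0.450 | 0.744 | 0.040 |
| 20% | 0.400 | 0.508 | 0.014 |
| 30% | 0.350 | 0.264 | 0.004 |

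Under the alternative about 39 × 0.50 = 19.5 patients survive 6 months, so 10% is about two patients.

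**3. Unknown status, patient replaced.** This could follow from the first 8.1 sentence. Let s be the share of survivors who have progressed, t the share of deaths preceded by progression, and q the share of progressors lost; all three are assumptions. The rate among those counted is p(1 − qs) / [p(1 − qs) + (1 − p)(1 − qt)].

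- s = 0.5, t = 0.8, q = 0.25, p = 0.30: 0.2625 / (0.2625 + 0.56) = 0.319, so type I error is 0.147. With q = 0.10 it is 0.111, and with q = 0.50 it is 0.259.
- s = 0.8, t = 0.6, q = 0.25, p = 0.30: 0.24 / (0.24 + 0.595) = 0.287, so type I error is 0.068. At p = 0.50 the rate is 0.4 / (0.4 + 0.425) = 0.485, so power is 0.863.
- s = t: no change.

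The direction depends on whether progression is more common among those who die or those who survive.

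**4. Kaplan-Meier estimate censored at progression (worst case).** Assume constant hazards, a progression-free survival (PFS) median of 1.9 months (the colorectal figure in 1.3.2), and a fraction f = 0.1 to 0.3 of PFS events being deaths without prior progression. The PFS hazard is ln 2 / 1.9 = 0.365 per month, and PFS(6) = exp(−6 × 0.365) = 0.112.

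- Share withdrawn alive by 6 months: (1 − f)(1 − 0.112) = 80% to 62%, or 31 to 24 of 39.
- Kaplan-Meier reading at 6 months: exp(−6 × f × 0.365) = 0.80, 0.65 and 0.52 for f = 0.1, 0.2 and 0.3, when true OS is 30%.

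With the 4.8-month GIST median from 1.3.2, PFS(6) = 0.420. The withdrawn share is 52% to 41% (20 to 16 of 39), and the reading is 0.92 to 0.77 when true OS is 50%. True OS of 30% is not possible there, since OS cannot be below PFS.

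**The case against.** The strongest reply is that intent is documented. The calendar has a dedicated post-progression column with its own footnote, 8.1 commits to at least 6 months of follow-up, 8.2 holds the final analysis until the last patient passes 6 months, and section 10 mentions subjects in follow-up after the study. A site must put a general list above a specific schedule to lose these data, and deaths may still be found in records. This stands: the harm is conditional and the documents give no rate for it. It does not remove the contradiction, and clear intent makes correcting 4.2.1 easy.

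Three stronger readings are tempting and not supported.

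- A reader might infer that anyone stopping for toxicity or by investigator decision falls under no follow-up rule. Toxicity as such is not a listed reason in 4.2.1, and the calendar has a pre-progression follow-up column in which such a patient can remain until footnote 2 applies. Someone leaving by investigator decision alone is a dropout under 4.2.2 and is replaced, so the counts do not need that patient's status. What remains for toxicity is the dose-reduction wording in 5.1.4.1.
- A reader might infer that the protocol never separates leaving treatment from leaving the study. Footnote 2 and Tables 6.3 and 6-4 do refer to treatment or protocol therapy only. The distinction exists but is missing from 4.2.1.
- A reader might infer that the trial's conclusion would be biased upward. That holds for a Kaplan-Meier curve censored at progression. The go/no-go rule is a binomial count, for which the error can go either way.

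**Conclusion.** The contradiction between 4.2.1 and calendar footnote 2 is in the text, and so is the off-trial versus off-protocol-therapy conflict after more than two dose reductions. Both bear on patients whose 6-month status the primary analysis needs, so the wording should be corrected.

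The size is conditional. The count rule is sensitive to even one or two survivors with unknown status who are not counted: about one (5%) takes power to 0.834 and about two (10%) to 0.744. If lost progressors are replaced, type I error ranged from 0.068 to 0.259 under the assumptions shown. The Kaplan-Meier readings of 52–80% against a true 30% are a worst case: every site stops at progression, no later death is found, the PFS median is borrowed from another tumour, and the share of PFS events that are deaths is assumed. They are not a forecast for this trial. If vital status is followed for everyone, the design keeps its stated properties (type I error 0.0943, power 0.9001).

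**What to change.** - In 4.2.1, state that progression, and any other reason that leaves the patient evaluable (including severe toxicity), does not end vital-status follow-up. Follow-up continues to at least 6 months from starting on trial and then as in footnote 2, unless the patient dies, withdraws consent to follow-up or is lost.
- Word calendar footnote 2 so that survival follow-up starts after coming off treatment for any reason.
- Reconcile the text of 5.1.4.1 with the footnotes of Tables 6.3 and 6-4 on more than two dose reductions, for follow-up purposes only. All treatment and stopping rules stay as they are.

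Sample size and cut-offs do not change. The cost is an amendment of wording and a few extra vital-status checks in patients already off treatment. Making the two evaluability sentences in 8.1 agree is a related edit that would settle how any status still unknown is handled.

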4.2.2 Screen Failures/Dropouts

A subject who discontinues study participation prematurely for any reasons except death, disease progression and severe toxicity is defined as a dropout.

A subject who, for any reason (e.g. failure to satisfy the selection criteria), terminates the study before the time point used for the definition of “dropout” (see above) is regarded a “screening failure”.

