4.2.3 Replacement

Dropout patients will need to be replaced.

Patients will be considered inevaluable for the primary endpoint of 6 month of OS if they are not able to complete first cycle. Inevaluable patients will be replaced

5. Treatment[s]

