8.2 Statistical Analysis

Overall survival (OS) is defined as the time from starting on trial to date of death due to any cause and progression-free survival (PFS) is defined as the duration of time from start of treatment to time of progression or death, whichever comes first. The final analysis will be conducted after the follow-time of the last patient exceeds 6 months. The primary endpoint of the study is OS at 6 month. The experimental treatment will be deemed to have good activity if ≥ 16 out of 39 evaluable patients survive 6 months or more. OS will be estimated using the Kaplan-Meier method and the two-sided 95% confidence interval (CI) for median OS will be computed using log-log transformation.

The secondary endpoints in this study include the disease control response (DCR) defined as (CR + PR+ SD), toxicity, and PFS. DCR rate will be reported with 95% CI computed by the Clopper-Pearson method. The frequency and severity of adverse events and tolerability of the regimen will be summarized using descriptive statistics. PFS with 95% CI will be estimated. As exploratory objective, the association between biomarkers and clinical outcomes (DCR rate, OS and PFS) will be examined using multiple logistic regression and the multivariable Cox regression model. A p-value of < 0.05 will be considered statistically significant. Frequency and severity of adverse events will be summarized using descriptive statistics.

9. Safety Monitoring

Safety assessments will consist of monitoring and recording all adverse events and serious adverse events, the regular monitoring of hematology and blood chemistry parameters and regular physical examinations. Adverse events will be evaluated continuously throughout the study. Safety and tolerability will be assessed according to the NIH/NCI Common Terminology Criteria for Adverse Events version 4.0 (CTCAE v4.0) that is available at:

<http://evs.nci.nih.gov/ftp1/CTCAE/About.html>

The PMC monitors its assigned ongoing research protocols for: adverse event reporting, data and safety monitoring, and internal audit findings. The PMC, upon review of any

agenda item, may approve the study for continuation, require revisions, suspend or close a protocol.

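### Treated patients who drop out, are lost before 6 months or do not complete cycle 1 are replaced in the 6-month OS count, so the stated 10% type I error is not assured

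*Combined protocol and SAP*

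**What the plan says.** Section 8.2 defines OS from starting on trial to death from any cause. Activity is declared if at least 16 "out of 39 evaluable patients survive 6 months or more". Section 8.1 sets the stage 1 rule at 8 of 28. Three rules take treated patients out of these counts and replace them.

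1. **Dropouts.** Section 4.2.2: "A subject who discontinues study participation prematurely for any reasons except death, disease progression and severe toxicity is defined as a dropout". Sections 4.2.3 and 8.1 replace them. Section 4.2.1 lists reasons that can lead to this status without death, documented progression or severe toxicity. They include withdrawn consent, the investigator's judgement that continuing would be harmful, intercurrent illness, and "Deterioration of ECOG performance status to 3 or 4".
2. **Lost before 6 months.** Section 8.1 states this rule twice, with different exemptions. The first version covers patients lost to "follow-up prior to 6 months from starting on trial except death are not evaluable for the primary endpoint". The second reads "lost follow-up prior to 6 months from starting on trial except death, disease and severe toxicity are not evaluable for the primary endpoint".
3. **Cycle 1 not completed.** Section 4.2.3: "Patients will be considered inevaluable for the primary endpoint of 6 month of OS if they are not able to complete first cycle". They are replaced, and the sentence has no exemption.

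On follow-up, Section 4.2.1 makes progression a mandatory reason to leave both treatment and procedures. Calendar footnote 2 in Section 6.1 says that assessments after progression "should take place every 3 months for up to two years or death". Footnote 1 ends the scheduled parameters at progression or at any withdrawal under 4.2.1. No survival follow-up is therefore scheduled for a patient who leaves without progression.

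**The concern.** Replacing an inevaluable patient can be defended for an endpoint that needs a scan. Six-month survival needs only the knowledge that the patient is alive or dead, which can usually be learned without treatment or visits. Removal after the first dose selects on events that may be related to prognosis.

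The direction of the bias depends on who is removed. If removed patients survive less well than the rest, survival among evaluable patients is too high. If they survive better, it is too low. The clearest upward route is the cycle 1 sentence: a patient who dies in cycle 1 is a certain failure, yet read literally is replaced.

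The wording of 8.1 adds a second ambiguity. It is unclear whether its exemption for death covers dropouts or only lost patients. If it covers dropouts, those who die count as failures while those who survive are removed, and the bias is downward. Two statisticians could build different denominators from the same data and reach different decisions on the primary endpoint.

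**Working it through.** **Inputs from Section 8.1.** Null 30%, alternative 50%; 28 patients in stage 1 and 11 in stage 2; go on if at least 8/28; declare activity if at least 16/39; one-sided type I error 10%, power 90%.

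**Step 1: reproduce the plan.** With true survival p in the counted patients, the exact probability of declaring activity is

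R(p) = Σ (x from 8 to 28) P(X₁ = x) · P(X₂ ≥ 16 − x), with X₁ ~ Bin(28, p) and X₂ ~ Bin(11, p).

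R(0.30) = 0.0943 and R(0.50) = 0.9001, so the stated design is correct. R(p) passes 0.10 once p exceeds 0.3023, so there is little slack.

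**Step 2: all removed patients replaced.** Let q be the share of treated patients removed and s their 6-month survival. The plan gives neither, so both are assumptions. If survival in all treated patients is 30%, survival in the evaluable patients is

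p = (0.30 − q·s) / (1 − q).

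Example: q = 0.10, s = 0.20 gives p = (0.30 − 0.02)/0.90 = 0.3111 and R = 0.123.

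Probability of declaring activity at a true 30%:

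| Share removed | s = 0 | s = 10% | s = 20% | s = 30% | s = 40% |
|---|---|---|---|---|---|
| 5% | 0.137 | 0.122 | 0.107 | 0.094 | 0.082 |
| 10% | 0.196 | 0.157 | 0.123 | 0.094 | 0.071 |

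The 10% level is passed once q exceeds 0.8% (s = 0), 1.2% (s = 10%) or 2.3% (s = 20%).

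**Step 3: cycle 1 rule read literally.** Early deaths have s = 0, so p = 0.30/(1 − q).

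- q = 3%: p = 0.3093, R = 0.118
- q = 5%: p = 0.3158, R = 0.137
- q = 10%: p = 0.3333, R = 0.196

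Section 8.1 uses an exponential model for its hazard ratio. Under the null that model puts 1 − 0.30^(28/182.6) = 16.9% of patients dead by day 28. Then p = 0.30/0.831 = 0.361 and R = 0.313. This is an outer figure: the inclusion criterion of at least 12 weeks' life expectancy makes fewer early deaths plausible.

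**Step 4: the other reading of 8.1.** If dropouts who die are kept and only surviving dropouts are removed, p = (P − q·s)/(1 − q·s), where P is survival in all treated patients. Take 10% dropouts with average survival (s = P).

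- P = 0.30: p = 0.27/0.97 = 0.2784, R = 0.052
- P = 0.50: p = 0.45/0.95 = 0.4737, R = 0.830

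Type I error is then conservative and power is below the stated 90%.

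**The case against.** The strongest defence is that Section 8.1 governs evaluability for this endpoint and exempts death in both of its sentences, so a sensible analyst would count a cycle 1 death. On that reading the figures for replaced early deaths do not arise. The 0.313 also needs a constant hazard from day 0 in patients selected for ECOG 0 or 1 and a 12-week life expectancy. This has force: 0.313 should not be taken as an expected value. But 4.2.3 as written says otherwise, and bringing it into line with 8.1 is itself one of the edits needed.

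For dropouts and lost patients, 4.2.2 already excludes death, progression and severe toxicity, so assuming that none of them survives is too harsh. With 20% survival the inflation is modest (0.107 and 0.123), and with survival above 30% the error falls. The word for disease in the second 8.1 sentence might also cover cancer-related ECOG decline. This stands: for these two rules even the direction is unknown. It supports saying that the error rate is not assured, and no more.

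Finally, the synopsis already plans a Kaplan-Meier estimate of 6-month OS, which could censor losses. But the decision is a count among evaluable patients, and no all-treated population is specified for either analysis.

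**Conclusion.** The concern holds. The design arithmetic is right (0.094 and 0.900), but those figures apply to the evaluable count only if removal is unrelated to 6-month survival. With 5% to 10% removed, the type I error runs from 0.107 to 0.123 if the removed patients have 20% survival and from 0.137 to 0.196 if none survives. It falls to 0.082 and 0.071 if they have 40% survival. Under the other reading of 8.1, with 10% dropouts, it is 0.052 with power 0.830. Removal rates and survival are assumptions throughout.

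The conflict between 4.2.3 and the exemptions in 4.2.2 and 8.1 does not depend on any assumption. The conflict between 4.2.1 and calendar footnote 2 is one of wording only, because progressed patients stay in the denominator. The point should be corrected before the primary analysis.

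**What to change.** - Define the primary population as every patient who took at least one dose, with no replacement after the first dose.
- Delete the cycle 1 inevaluability sentence in 4.2.3 as it applies to OS. Keep a single exemption sentence in 8.1, or none once replacement is dropped.
- In 4.2.1, separate stopping treatment from ending survival follow-up, and reconcile it with calendar footnote 2.
- Collect vital status to at least 6 months for all treated patients except those who refuse survival follow-up.
- Apply 8/28 and 16/39 to the first 28 and 39 treated patients, counting unknown 6-month status as not surviving.
- Specify the planned Kaplan-Meier 6-month estimate on the same population, censored at last contact, as the sensitivity analysis.

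**Cost.** No added patients. Vital-status checks by phone or records are new for patients who leave without progression, but light. With complete vital status the error and power remain 0.094 and 0.900. Counting unknowns as failures is conservative. If a share u is unknown independently of survival, p becomes P(1 − u):

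| Unknown | Type I error | Power |
|---|---|---|
| 2% | 0.081 | 0.876 |
| 5% | 0.063 | 0.834 |
| 10% | 0.040 | 0.744 |

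The stated power is therefore kept only if follow-up for vital status is nearly complete.
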